- The study drug can be administered with/without food. The study drug will be administered orally using a dosing syringe.
- Clinical evaluation includes measurements/evaluations of respiratory rate, heart rate, body temperature, and SpO₂, need for and duration of rehospitalization, occurrence of complications, need for antibiotics. In case antipyretics are used, body temperature should be measured immediately before or >4 hours after giving

antipyretics. Parents/caregivers should be instructed accordingly. All clinical assessments should preferably be done when the infant is calm (ie, not crying or immediately after feeding).

- g. If the subject is enrolled in the substudy of Study 53718678RSV2002 (see Section 3.1), the same parameters as assessed by the biosensor will be recorded from the standard-of-care monitoring/assessments as part of the substudy assessments (refer to the substudy Clinical Protocol for detailed information).
- h. Only applicable in case of on-site visit.
- i. The clinician PRESORS ([Attachment 4](#)) has to be completed by the clinician on the electronic device.
- j. Detailed information is available in Section 9.2.2.
- k. The morning assessment needs to be done prior to discharge and the evening one should be done at home.
- l. If the subject is discharged prior to completion of the last assessment of the bid schedule, this last assessment should be performed at home.
- m. The parent(s)/caregiver(s) PRESORS ([Attachment 5](#)) has to be completed by the subject's parent(s)/caregiver(s) during end-of-study visit as the first activity of the visit prior to any other procedures.
- n. Mid-turbinate swabs should be collected from the same nostril throughout the study (unless precluded due to bleeding). After discharge, swabs will be collected daily through Day 8 in all subjects. As of Day 8, in subjects who were symptomatic based on the clinician PRESORS at Day 8, daily swabs will be collected through Day 13 or until the subject becomes asymptomatic based on the parent(s)/caregiver(s) PRESORS, as evaluated by the investigational staff (whichever comes first). On Day 14 and Day 21, a swab will be collected during the scheduled visit for all subjects. Detailed information on sample collection is available in Section 9.2.1.
- o. Leftover mid-turbinate nasal swab samples collected for other testing may be used for exploratory biomarker analyses, at discretion of the sponsor.
- p. To be completed by parent(s)/caregiver(s) on the electronic device (see [Attachment 7](#) [nasal swab log]), if applicable. Refer to Section 9.2.1 for detailed information.
- q. Body temperature to be measured by parent(s)/caregiver(s) and recorded on the electronic device (see [Attachment 8](#) [temperature log]). In case antipyretics are used, body temperature should be measured immediately before or >4 hours after giving antipyretics. Parents/caregivers should be instructed accordingly.
- r. On the day of discharge, if discharged in the morning, only the evening assessment of the bid schedule should be recorded in the temperature log on the electronic device.
- s. Systolic and diastolic blood pressure need to be measured sitting or supine (preferably the same position at each measurement) after at least 5 minutes of rest.
- t. Physical examination of all body systems includes length and head circumference and body weight measurement and skin examination.
- u. Directed physical examination includes respiratory system, nose, ear, throat, facial, and neck lymph nodes, and skin examination.
- v. Triplicate 12-lead ECGs will be obtained, approximately 1 minute apart and preferably all within 5 minutes. ECGs may be repeated at the discretion of the investigator. ECGs will be obtained in a supine position after 5 minutes of rest. If an ECG is scheduled at the same timepoint as other assessments, the ECG should be performed first.
- w. Samples for clinical laboratory assessments will be collected and analyzed at a central laboratory. Leftover blood samples collected for other testing may be used for exploratory biomarker analyses, at discretion of the sponsor.
- x. Urinalysis will be performed using dipsticks provided by the central laboratory. In case of abnormalities, the urine sample will be shipped to the central laboratory for flow cytometric and/or microscopic evaluation(s).
- y. Adverse events related to the use of the biosensor reported during the substudy will be recorded in the eCRF of the main study.

Note: Additional unscheduled visits in case of lab abnormalities, ECG abnormalities, need for clinical follow-up of (an) AE(s) can be scheduled at the discretion of the investigator.

COHORT 2 SUBJECTS RECRUITED AFTER PROTOCOL AMENDMENT 4^a

Phase	Screening	Treatment Phase							Follow-up ^b					
		1	2	3	4	5 (±1)	6-7	8 (+1)	9-13	14 (±1)	15-20	21 (±3)	22-27	28 (±3) End-of-study
Day	-1 to 1 ^c	1	2	3	4	5 (±1)	6-7	8 (+1)	9-13	14 (±1)	15-20	21 (±3)	22-27	28 (±3) End-of-study
	Screening / Predose On-site	Treatmen t On-site		On-site visit ^d		On-site visit ^d		On-site visit ^d		On-site visit ^d		On-site visit ^d		Phone visit/ Conditional ^e On-site visit ^d
Study Procedures														
Screening/Administrative														
Informed Consent	X													
Diagnostic ICF (optional) ^f	X													
Eligibility criteria ^g	X													
Subject characteristics and demographics	X													
Medical history/prior medications	X													
Local assay for RSV diagnosis ^h	X													
Randomization		X ⁱ												
Study Drug Administration														
Dosing study medication ^j		bid	bid	bid	bid	bid	bid	bid						
Provision of study drug for daily use at home ^k		X												
Document dosing in study medication log		bid ^l	bid	bid	bid	bid	bid	bid						
Checking of study medication log		X	X	X	X	X	X	X						
Efficacy Assessments														
Clinical evaluation ^m	X	X		X ⁿ		X ⁿ		X ⁿ		X ⁿ		X		(X) ^o

Phase	Screening	Treatment Phase								Follow-up ^b					
		1	2	3	4	5 (± 1)	6-7	8 (+1)	9-13	14 (± 1)	15-20	21 (± 3)	22-27	28 (± 3) End-of-study	
	Screening / Predose On-site	Treatment On-site	On-site visit ^d	Phone visit/ Conditional ^e On-site visit ^d											
Clinician PRESORS ^p	X	X		X		X		X		X		X			
Parent(s)/ caregiver(s) PRESORS ^q	X	bid	bid	bid	bid	bid	bid	bid	bid	bid	X	X ^r			
Monitoring of parent(s)/caregiver(s) PRESORS completion by the site staff	X	X	X	X	X	X	X	X	X	X	X	X			
Mid-turbinate nasal swab: RSV diagnosis confirmation, RSV viral load, presence of other viral or bacterial pathogens, viral sequencing (centrally) ^{s,t,u}	X ^v														
Mid-turbinate nasal swab: RSV viral load, viral sequencing ^{t,u}			X	X	X	X	X	X	X	X		X			
Nasal swab log ^w			X		X		X		X						
Temperature log ^x	X	bid	bid	bid	bid	bid	bid	bid	bid	bid	X	X			
Medical resource utilization	X	X	X	X	X	X	X	X	X	X	X	X	X	X	
Safety Assessments															
Systolic and diastolic blood pressure ^y	X			X		X		X		X		X		(X) ^o	
Physical examination (all body systems) ^z	X														
Directed physical examination ^{aa}				X				X		X		X		(X) ^o	

Phase	Screening	Treatment Phase							Follow-up ^b					
		1	2	3	4	5 (± 1)	6-7	8 (+1)	9-13	14 (± 1)	15-20	21 (± 3)	22-27	28 (± 3) End-of-study
Day	-1 to 1 ^c													
	Screening / Predose On-site	Treatmen t On-site		On-site visit ^d		On-site visit ^d		On-site visit ^d		On-site visit ^d		On-site visit ^d		Phone visit/ Conditional ^e On-site visit ^d
ECG (triplicate 12-lead) ^{bb}	X	X ^{gg}		X ^{gg}				X				X ^{gg}		(X) ^{o,gg}
Clinical Laboratory Assessments														
Blood sampling for hematology and biochemistry ^{cc}	X ^{hh}							X ^{hh}				X		(X) ^o
Urinalysis ^{dd}	X							X				X		(X) ^o
Pharmacokinetics														
Blood sampling for pharmacokinetics of JNJ-53718678 ^{ee}		X ⁱⁱ		(X) ⁱⁱ		(X) ⁱⁱ								
Acceptability/Palatability														
Acceptability/ palatability questionnaire for parent(s)/caregiver(s)								X						
Ongoing Subject Review														
Adverse events ^{ff}	X	X	X	X	X	X	X	X	X	X	X	X	X	X
Concomitant medication	X	X	X	X	X	X	X	X	X	X	X	X	X	(X) ^o

- When subjects are hospitalized during the course of the study, the reason for hospitalization should be recorded and every effort should be made by the investigator to perform all the assessments as indicated in the **TIME AND EVENTS SCHEDULE**, if practically feasible.
- In case subjects prematurely discontinue study drug treatment for any reason (except withdrawal of consent), the parent(s)/caregiver(s) will be asked to continue with the subject's remaining study visits and assessment schedule, or, at a minimum, to return with the subject to the site for a Withdrawal and a Safety Follow-up Visit. At the Withdrawal and Safety Follow-up Visits, the same assessments as on the Day 8 and Day 21 visits, respectively, will be performed. In case the subject's legally acceptable representative(s) withdraw consent during the treatment or follow-up phase, an optional Withdrawal and Safety Follow-up Visit will be offered. At these optional Withdrawal and Safety Follow-up Visits, the same assessments as on the Day 8 and Day 21 visits, respectively, will be performed.
- Screening/predose assessments can only start after signing of the ICF and before randomization. All screening/predose procedures should take place prior to the first study drug intake.
- If feasible for the study site and if allowed per local regulations, home visits are allowed instead of on-site visits (although on-site visits are preferred).
- Subject's parent(s)/caregiver(s) will be contacted by site staff for a telephone follow up visit. In case a subject is experiencing (an) ongoing AE(s) or has clinically significant laboratory or ECG abnormalities at the time of the Day 21 follow-up visit, parent(s)/caregiver(s) might be requested, at the discretion of the investigator,

to have a Safety Follow-up Visit for the subject at the site (preferred option) or, if feasible for the study site and if allowed per local regulations, at home on Day 28 (± 3). Only clinically relevant assessments will be performed during this visit.

- f. Prior to signing the main consent form for the study, subject's legally acceptable representative may specifically allow for the collection and testing of nasal mid-turbinate swab by signing the pre-screening (diagnostic) ICF. This is not required if a positive RSV diagnostic result based on a local SOC sample collected within 48 hours prior to anticipated randomization is available and used for determining study eligibility.
- g. Investigators should ensure that all study enrollment criteria have been met at screening. If a subject's clinical status changes (including any available laboratory results or receipt of additional medical records) after screening but before the first dose of study drug is given such that they no longer meet all eligibility criteria, they should be excluded from participation in the study.
- h. During screening, a study-specific screening sample (mid-turbinate swab) will be collected for the local diagnosis of RSV infection using a preferably rapid PCR- or other molecular-based diagnostic assay (preferred) or a rapid-antigen-detection assay. Swabs collected per local SOC testing within 24 hours prior to start of screening may be used in determining study eligibility. If a rapid-antigen-detection assay is used as part of SOC or study-specifically (with the main study ICF or with the diagnostic ICF having been signed), the remainder of the screening sample used for the RSV diagnostic testing should be sent to the central laboratory for additional virologic analyses, as applicable.
- i. Randomization should occur within 24 hours after start of screening or within 48 hours after collection of the SOC sample used for local RSV diagnosis, whichever comes first. Randomization is to occur predose.
- j. Study drug administration should start as soon as possible, but no later than 4 hours after randomization and within 5 days after symptom onset. For analysis purposes, the day of first study drug intake will be considered Day 1. Dosing should preferably occur approximately at the same time each day for both intakes (AM and PM). For subjects who receive only 1 dose of JNJ-53718678 or placebo PM on Day 1, dosing should continue through the morning (ie, AM) of Day 8 so that all subjects receive 14 consecutive doses in total. Administration of the second dose may be delayed or brought forward (by maximum 4 hours) only if the nominal timing for this second dose falls in the middle of the night; thereafter, further dosing will follow a regular AM/PM dosing schedule. The study drug can be administered with/without food. The study drug will be administered orally using a dosing syringe.
- k. Study site personnel will instruct subjects' parent(s)/caregiver(s) on how to use and store the study drug for at-home dosing. Study drug will be provided in 1 single vial, from which the assigned volume is to be withdrawn each day.
- l. Date and time of study medication dosing has to be recorded, also in case if it cannot be recorded in the study medication log by the site.
- m. Clinical evaluation includes measurements/evaluations of respiratory rate, heart rate, body temperature, and SpO₂, need for and duration of hospitalization, occurrence of complications, need for antibiotics. In case antipyretics are used, body temperature should be measured immediately before or >4 hours after giving antipyretics. Parents/caregivers should be instructed accordingly. All clinical assessments should preferably be done when the infant is calm (ie, not crying or immediately after feeding). In case Cohort 2 Screening and Randomization occur on the same calendar day, clinical evaluation does not have to be repeated.
- n. If the subject is enrolled in the substudy of Study 53718678RSV2002 (see Section 3.1), heart rate, respiratory rate, and SpO₂ will be recorded as part of the substudy assessments (refer to the substudy Clinical Protocol for detailed information).
- o. Only applicable in case of on-site visit.
- p. The clinician PRESORS ([Attachment 4](#)) has to be completed by the clinician on the electronic device.
- q. An electronic device will be provided to the subject's parent(s)/caregiver(s) during screening and the investigator/study site personnel will provide sufficient information to enable the subject's parent(s)/caregiver(s) to complete these assessments. The first parent(s)/caregiver(s) PRESORS ([Attachment 5](#)) assessment of the bid schedule on Day 1 needs to be completed as close as feasible and prior to the first administration of study drug. Detailed information is available in Section 9.2.2.
- r. The parent(s)/caregiver(s) PRESORS has to be completed by the subject's parent(s)/caregiver(s) during end-of-study visit as the first activity of the visit prior to any other procedures.
- s. One mid-turbinate nasal swab will be taken of which aliquots will be used for the central laboratory confirmation of RSV infection, to determine RSV viral load, to determine mutations in the viral genome potentially associated with resistance to JNJ-53718678, and to determine the presence of other viral or bacterial pathogens.

- t. Mid-turbinate swabs should be collected from the same nostril throughout the study (unless precluded due to bleeding). Swabs will be collected daily through Day 8 in all subjects. The investigator/study site personnel will train the parent(s)/caregiver(s) to collect the mid-turbinate nasal swab in case collection by an HCP is not possible. As of Day 8, in subjects who were symptomatic based on the clinician PRESORS at Day 8, daily swabs will be collected through Day 13 or until the subject becomes asymptomatic based on the parent(s)/caregiver(s) PRESORS, as evaluated by the investigational staff (whichever comes first). On Day 14 and Day 21, a swab will be collected during the scheduled visit for all subjects. Detailed information on sample collection is available in Section 9.2.1.
- u. Leftover mid-turbinate nasal swab samples collected for other testing may be used for exploratory biomarker analyses, at discretion of the sponsor.
- v. The baseline mid-turbinate nasal swab should be collected as close as possible and prior to the first administration of study drug (on Day 1). If a study-specific screening nasal mid-turbinate swab was collected within 8 hours prior to dosing, the leftover of that sample can serve as the baseline sample and should be shipped to the central laboratory, provided that the study-specific nasal mid-turbinate screening sample was stored appropriately and has sufficient sample volume available (minimum 4 aliquots of 600 µL).
- w. To be completed by parent(s)/caregiver(s) on the electronic device (see [Attachment 7](#) [nasal swab log]), if applicable. Refer to Section 9.2.1 for detailed information.
- x. Body temperature to be measured by parent(s)/caregiver(s) and recorded on the electronic device (see [Attachment 8](#) [temperature log]). In case antipyretics are used, body temperature should be measured immediately before or >4 hours after giving antipyretics. Parents/caregivers should be instructed accordingly.
- y. Systolic and diastolic blood pressure need to be measured sitting or supine (preferably the same position at each measurement) after at least 5 minutes of rest.
- z. Complete physical examination of all body systems includes length and head circumference and body weight measurement and skin examination.
- aa. Directed physical examination includes respiratory system, nose, ear, throat, facial, and neck lymph nodes, and skin examination.
- bb. Triplicate 12-lead ECGs will be obtained, approximately 1 minute apart and preferably all within 5 minutes. ECGs may be repeated at the discretion of the investigator. ECGs will be obtained in a supine position after 5 minutes of rest. If an ECG is scheduled at the same timepoint as other assessments, the ECG should be performed first.
- cc. Samples for clinical laboratory assessments will be collected and analyzed at a central laboratory. Leftover blood samples collected for other testing may be used for exploratory biomarker analyses, at discretion of the sponsor. Subjects can start treatment before the laboratory results are available (see also Section 9.1.2).
- dd. Urinalysis will be performed using dipsticks provided by the central laboratory. In case of abnormalities, the urine sample will be shipped to the central laboratory for flow cytometric and/or microscopic evaluation(s).
- ee. Blood samples for determination of JNJ-53718678 concentrations will be collected through finger prick or heel stick on Days 3 and 5 at a random timepoint (predose or postdose) during the visit. Detailed information on sample collection is available in Section 9.4. Leftover blood samples collected for other testing may be used for exploratory biomarker analyses, at discretion of the sponsor.
- ff. Adverse events related to the use of the biosensor reported during the substudy will be recorded in the eCRF of the main study.
- gg. At Day 1 and Day 3, ECGs should be obtained approximately one hour after administration of study drug. At Day 28, ECGs should be obtained in case abnormal ECGs at Day 21 or at discretion of the principal investigator. Anytime when it is clinically indicated or for confirmation of abnormal ECG findings, unscheduled ECGs should be obtained.
- hh. Levels of potassium and magnesium will be determined by the central laboratory. In case of hypokalemia or hypomagnesemia at screening or at Day 8, the levels of potassium and magnesium should be checked as soon as possible at the local laboratory and corrected to prevent cardiac disturbances. Appropriate clinical management per local SOC (including but not limited to checking the corrected values at local laboratory) may be required.
- ii. PK samples should be collected approximately one hour after administration of study drug (after the ECGs are obtained if applicable) at Day 1 and at least 4 hours after the AM and prior to the PM dosing on Day 3 or Day 5.

Note 1: Additional unscheduled visits in case of lab abnormalities, ECG abnormalities, need for clinical follow up of (an) AE(s) can be scheduled at the discretion of the investigator.

Note 2: Refer to [Attachment 10](#) for guidance on study conduct during the COVID 19 pandemic.

ABBREVIATIONS

AE	adverse event
ALT	alanine transaminase
AST	aspartate aminotransferase
aPTT	activated partial thromboplastin time
AUC	area under the RSV viral load-time curve
BCRP	breast cancer resistance protein
bid	twice daily
BM	bone marrow
BW	body weight
CI	confidence interval
C _{max}	maximum plasma concentration
C _{min}	minimum plasma concentration
COA	clinical outcome assessment (paper or electronic as appropriate for this study)
COVID-19	Coronavirus Disease 2019
CPE	complete physical examination
(e)CRF	case report form(s) (paper or electronic as appropriate for this study)
CV	coefficient of variation
CYP	cytochrome
DBP	diastolic blood pressure
DMC	Data Monitoring Committee
DMID	Division of Microbiology and Infectious Diseases
DPE	directed physical exam
EC ₅₀	effective concentration for 50% inhibition
ECG	electrocardiogram
eDC	electronic data capture
FC	food consumption
GCP	Good Clinical Practice
GGT	γ-glutamyltransferase
GLP	Good Laboratory Practice
GPT	glutamic-pyruvic transaminase
HCP	healthcare provider
HIV	human immunodeficiency virus
HP-β-CD	2-Hydroxypropyl-beta-cyclodextrin
ICF	informed consent form
ICH	International Conference on Harmonisation
ICU	intensive care unit
IDMC	independent data monitoring committee
IEC	Independent Ethics Committee
IPPI	investigational product preparation instruction
IRB	Institutional Review Board
IV	intravenous
IWRS	interactive web response system
LC-MS/MS	liquid chromatography/mass spectrometry/mass spectrometry
LLOQ	lower limit of quantification
LRTI	lower respiratory tract infection
MATE1	multidrug and toxin extrusion 1
MCP-Mod	Multiple Comparison Procedure-Modeling
MDE	multiple-dose escalation
MedDRA	Medical Dictionary for Regulatory Activities
MTD	maximum tolerated dose
NOAEL	no observed adverse effect level
OAT	organic anion transporter
OATP	organic-anion-transporting polypeptide
OCT	organic cation transporter
PCR	polymerase chain reaction

PD	pharmacodynamic(s)
PK	pharmacokinetic(s)
PND	post-natal day
popPK	population pharmacokinetic(s)
PQC	Product Quality Complaint
PRESORS	Pediatric RSV Electronic Severity and Outcome Rating Scales
PRO	patient-reported outcome(s) (paper or electronic as appropriate for this study)
PT	prothrombin time
qd	once daily
qRT-PCR	quantitative reverse transcription polymerase chain reaction
QTcB	QT interval corrected for heart rate according to Bazett's formula
QTcF	QT interval corrected for heart rate according to Fridericia's formula
QTcI	individual-corrected QT interval
RBC	red blood cell
RSV	respiratory syncytial virus
SAE	serious adverse event
SAP	statistical analysis plan
SBP	systolic blood pressure
SDE	single-dose escalation
SOC	standard of care
SUSAR	suspected unexpected serious adverse reaction
TEAE	treatment-emergent adverse event
TQT	thorough QT
URTI	upper respiratory tract infection
WBC	white blood cell

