The basis of the sample size calculation is the antiviral results of Study 53718678RSV1005. In that study, the mean difference in RSV viral load AUC from baseline until Day 5 of the placebo group versus active (adjusted for baseline viral load) was estimated as 105 \log_{10} copies.hour/mL (corresponding to a 25% reduction) and the standard deviation (SD) on the RSV viral load AUC as 85 \log_{10} copies.hour/mL (corresponding to a coefficient of variation [CV] of approximately 20%).

Assuming a more conservative reduction in RSV viral load AUC of 20% compared to placebo, considering a CV of 35% (slightly higher variability than observed in Study 53718678RSV1005), and a 1-sided alpha of 2.5%; the power to conclude a dose-response using the Multiple Comparison Procedure-Modeling (MCP-Mod) procedure under different assumptions for the dose-response relationship (linear, E_{max} , and

exponential) is provided in the table below. Based on Study 53718678RSV1005 results, no discrimination between the proposed doses is expected (ie, E_{max} dose-response shape was observed).

Table Power (%) to Conclude Dose-response Using MCP-Mod Under Different Assumptions for the Dose-response Relationship

Assumed CV	Assumed dose-response relationship		
	Linear	E_{max}	Exponential
	Cohort 1 + Cohort 2 (N=74 per treatment arm)		
20%	100.0	100.0	100.0
35%	92.3	95.3	96.6
Cohort 2 only (N=50 per treatment arm)			
20%	99.8	100.0	100.0
35%	79.0	84.0	86.9
Cohort 1 only (N=24 per treatment arm)			
20%	91.5	94.7	96.2
35%	47.1	51.2	54.7

If data of both cohorts are combined (N=74 per treatment arm), the power to conclude dose-response is more than 90% for all 3 different assumptions for the dose-response relationship. If data from Cohort 1 cannot be combined with data from Cohort 2 (eg, due to inconsistency [means and/or variability] in viral load data between cohorts per treatment group), the power to conclude a dose-response using the MCP-Mod procedure in Cohort 2 (N=50 per treatment arm) is at least 79%.

The sample size in Cohort 1 only ($n \geq 24$ per treatment arm) will provide sufficient power (approximately 90%) if the reduction in RSV viral load AUC is at least 20% with a CV which is not higher than observed in Study 53718678RSV1005 (ie, 20%).

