Study drug administration should start as soon as possible, but no later than 4 hours after randomization and within 5 days after symptom onset. For analysis purposes, the day of first study drug intake will be considered Day 1. Dosing should preferably occur approximately at the same time each day for both intakes (AM and PM). For subjects who receive only 1 dose of JNJ-53718678 or placebo PM on Day 1, dosing should continue through the morning (ie, AM) of Day 8 so that all subjects receive 14 consecutive doses in total. Administration of the second dose may be delayed or brought forward (by maximum 4 hours) only if the nominal timing for this second dose falls in the middle of the night; thereafter, further dosing will follow a regular AM/PM dosing schedule. JNJ-53718678/placebo can be administered with/without food. The study drug will be administered orally using a dosing syringe. For Cohort 1 and during hospitalization, the study drug can also be administered through a nasogastric tube, if already in place. In this document, both administration methods are referred to as “oral dosing”, unless specified otherwise.

Note: Prior to Protocol Amendment 4, the total daily dose was the same but the daily dosing frequency was qd instead of bid.

For dosing purposes, 3 age groups are defined depending on the subject’s age at the time of consent:

- Age group 1: ≥ 28 days and < 3 months of age (28 to 91 days of age, extremes included, for IWRS purposes)
- Age group 2: ≥ 3 months and < 6 months of age (92 to 182 days of age, extremes included, for IWRS purposes)
- Age group 3: ≥ 6 months and ≤ 3 years of age (183 to 1,096 days, extremes included, for IWRS purposes).

Study drug will be administered twice daily for 7 days (14 consecutive doses). Doses are based on weight and age group:

- High Dose (Cohort 1: n = 48 [target]; Cohort 2: n = 50 [target]):
 - Age group 1: 2.5 mg JNJ-53718678/kg bodyweight
 - Age group 2: 3.0 mg JNJ-53718678/kg bodyweight
 - Age group 3: 4.5 mg JNJ-53718678/kg bodyweight
- Low Dose (Cohort 1: n = 48 [target]; Cohort 2: n = 50 [target]):
 - Age group 1: 0.85 mg JNJ-53718678/kg bodyweight
 - Age group 2: 1.0 mg JNJ-53718678/kg bodyweight
 - Age group 3: 1.5 mg JNJ-53718678/kg bodyweight
- Placebo (Cohort 1: n = 48 [target]; Cohort 2: n = 50 [target]): those randomized to a placebo regimen will be subsequently randomized 1:1 to receive either:
 - High volume placebo:

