11.3. Sample Size Determination

11.3.1. Primary Objective: Establish Antiviral Activity

The basis of the sample size calculation is the antiviral results of Study 53718678RSV1005. In that study, the mean difference in RSV viral load AUC from baseline until Day 5 of the placebo group versus active (adjusted for baseline viral load) was estimated as $105 \log_{10}$ copies.hour/mL (corresponding to a 25% reduction) and the standard deviation (SD) on the RSV viral load AUC as $85 \log_{10}$ copies.hour/mL (corresponding to a CV of approximately 20%).

Assuming a more conservative reduction in RSV viral load AUC of 20% compared to placebo, considering a CV of 35% (slightly higher variability than observed in Study 53718678RSV1005), and a 1-sided alpha of 2.5%; the power to conclude a dose-response using the Multiple Comparison Procedure-Modeling (MCP-Mod) procedure under different assumptions for the dose-response relationship (linear, E_{max} , and exponential,) is provided in [Table 5](#). Based on Study 53718678RSV1005 results, no discrimination between the proposed doses is expected (ie, E_{max} dose-response shape was observed).

Table 5: Power (%) to Conclude Dose-response Using MCP-Mod Under Different Assumptions for the Dose-response Relationship

Assumed CV	Assumed dose-response relationship		
	Linear	E_{max}	Exponential
	Cohort 1 + Cohort 2 (N=74 per treatment arm)		
20%	100.0	100.0	100.0
35%	92.3	95.3	96.6
Cohort 2 only (N=50 per treatment arm)			
20%	99.8	100.0	100.0
35%	79.0	84.0	86.9
Cohort 1 only (N=24 per treatment arm)			
20%	91.5	94.7	96.2
35%	47.1	51.2	54.7

If data of both cohorts are combined (N 74 per treatment arm), the power to conclude dose-response is more than 90% for all 3 different assumptions for the dose-response relationship. If data from Cohort 1 cannot be combined with data from Cohort 2 (eg, due to inconsistency [means and/or variability] in viral load data between cohorts per treatment group), the power to conclude a dose-response using the MCP-Mod procedure in Cohort 2 (N 50 per treatment arm) is at least 79%.

The sample size in Cohort 1 only (N \geq 24 per treatment arm) will provide sufficient power (approximately 90%) if the reduction in RSV viral load AUC is at least 20% with a CV which is not higher than observed in Study 53718678RSV1005 (ie, 20%).

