11.4. Efficacy Analyses

[figure not shown]
The primary population for the efficacy/antiviral activity analysis will be the intent-to-treat infected population consisting of all randomized subjects who received at least one dose of study treatment and who have a centrally confirmed RSV viral load of $\geq 1 \log_{10}$ copies/mL above the LLOQ at baseline.

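### The "at least 79%" power for Cohort 2 alone holds only if all 50 enrolled per arm enter the ITT-infected primary population, and no exclusion allowance is stated

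*Protocol*

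**What the plan says.** The Sample Size part of the Synopsis and Section 11.3.1 both state, for the case in which the cohorts cannot be combined, that "the power to conclude a dose-response using the MCP-Mod procedure in Cohort 2 (N=50 per treatment arm) is at least 79"%. The matching block of Table 5 is labelled "Cohort 2 only (N=50 per treatment arm"), and at a CV of 35% it prints 79.0% (linear), 84.0% (Emax) and 86.9% (exponential). The planning effect is a 20% fall in viral load AUC relative to placebo, tested one-sided at the 2.5% level. On variability the same text speaks of "considering a CV of 35% (slightly higher variability than observed in Study 53718678RSV1005").

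Section 3.1 gives the enrollment target for each arm as "Cohort 2: n = 50 [target"]. Section 11.3.1 times the primary analysis by about 150 Cohort 2 subjects reaching Day 14 or discontinuing, so the trigger does not count analysable subjects.

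Section 11.4 defines the primary efficacy population as the "intent-to-treat infected population consisting of all randomized subjects who received at least one dose of study treatment", with the further condition that the central laboratory finds a baseline viral load at least 1 log10 copies/mL above the LLOQ. Section 11.3.1 then concludes that 72 subjects in Cohort 1 and 150 in Cohort 2 are enough even if the cohorts cannot be pooled.

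**The concern.** The same number, 50 per arm, serves as the enrollment target and as the analysed number in the power calculation, although the protocol defines the analysed set as a subset of those enrolled. Some loss is plausible on the protocol's own terms:

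- Entry needs only a positive local molecular or rapid-antigen test, with no viral-load threshold (Section 4.1).
- A qualifying standard-of-care swab may be up to 48 hours old at randomization, and dosing may follow up to 4 hours later.
- Up to 55% of subjects may enter more than 3 days after symptom onset, while the Introduction places peak viral load on average 3 days after onset.

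None of this yields a rate, but it makes an implicit rate of exactly zero hard to defend. At stake is the assurance that Cohort 2 can stand alone for the primary objective. That assurance rests on a stated minimum, and the minimum has no margin.

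**Working it through.** **Inputs.** From the Sample Size text: 20% reduction, CV 35%, 1-sided alpha 2.5%. From Section 11.4.1.1: doses 0, 3 and 9 mg/kg, three candidate shapes, and a maximum-of-contrasts t-test against a multivariate-t critical value. Allocation is 1:1:1. The shape parameters are not legible because the figure is not shown, so they were chosen to match Table 5: Emax with ED50 = 0.4 and exponential with delta = 1.2. Low-dose effects as fractions of the high-dose effect are then 1/3 (linear), 0.92 (Emax) and 0.006 (exponential).

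**Check on the CV.** Placebo mean = 105/0.25 = 420, and 85/420 = 20.2%. This agrees with the protocol's "corresponding to a coefficient of variation [CV] of approximately 20"%.

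**Formula.** With optimal unit-length contrasts c, the noncentrality for true shape s is (0.20/0.35) × √n × Σ c·s, with 3n − 3 degrees of freedom. For the linear contrast under a linear truth:

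- The centred shape is (−4/9, −1/9, 5/9), with length √(42/81) = 0.720.
- At n = 50 the noncentrality is 0.571 × 7.071 × 0.720 = 2.91, against a critical value of about 2.25.
- At n = 45 it is 2.76, and at n = 40 it is 2.60.

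Power is the probability that the largest of the three t statistics exceeds the critical value, obtained by simulation.

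**Reproducing the plan (n = 50, CV 35%).** 79.0/84.0/86.7%, against the printed 79.0/84.0/86.9%. With these shapes every cell of Table 5 is matched within about 0.4 points. Over a wide range of other shape parameters (ED50 0.3 to 3, delta 1.5 to 4.5) the linear cell at n = 50 stays between 78.9% and 81.1%.

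**Cohort 2 alone, CV 35%, exclusion rate assumed:**

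| Loss | Analysed per arm | Linear | Emax | Exponential |
|---|---|---|---|---|
| 0% | 50 | 79.0 | 84.0 | 86.7 |
| 2% | 49 | 78.2 | 83.2 | 86.0 |
| 5% | 47–48 | 76.4–77.3 | 81.5–82.4 | 84.4–85.2 |
| 10% | 45 | 74.5 | 79.7 | 82.7 |
| 20% | 40 | 69.3 | 74.6 | 77.8 |

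One exclusion per arm already puts the linear cell below 79%. The Emax cell stays above 79% up to about a 10% loss.

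**Combined cohorts, CV 35%:**

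| Starting n per arm | Loss | Analysed per arm | Linear | Emax | Exponential |
|---|---|---|---|---|---|
| 74 (Table 5) | 10% | 67 | 89.6 | 93.2 | 94.8 |
| 74 (Table 5) | 20% | 59 | 85.4 | 89.7 | 91.8 |
| 98 (48 + 50 planned) | 20% | 78 | 93.6 | 96.2 | 97.3 |
| 98 (48 + 50 planned) | 30% | 69 | 90.4 | 93.9 | 95.4 |

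**The case against.** The sentence is explicitly conditional on 50 per arm, and Table 5 reproduces, so there is no arithmetic slip. The affected figure is the worst cell of a contingency: cohorts that cannot be pooled, a linear shape, and a CV of 35%. The protocol expects an Emax shape, plans on a 20% reduction where 25% was observed, and uses a CV well above the roughly 20% observed. With 40 analysed per arm, power at CV 30% is still 82/87/89%, and at CV 20% it is at least 99%. Losses may be small, because every subject has a recent positive RSV test and the first dose is given or supervised by site staff within hours of randomization. All of this stands and limits the severity. It does not supply an allowance: CV 35% is the sponsor's own planning case, and a minimum was printed for it and relied on.

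Three stronger readings are tempting and unsupported:

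- A reader might infer that the analysis keeps only children with high viral load. The criterion is a floor of 1 log10 above the LLOQ, not a high-load selection.
- A reader might infer that Table 5 is out of date because it uses 24 per arm for Cohort 1 when the target is 48. The text presents these as minimums (N≥24 per arm, at least 72 subjects), and the rise to 48 served the precision of clinical-course estimates. Entering 48 would leave the Cohort 2 figure unchanged.
- A reader might infer that the trial is underpowered. With no exclusion rate in the document, that cannot be shown.

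**Conclusion.** The concern holds in a limited form. The 79% minimum for Cohort 2 alone is valid only if every enrolled subject qualifies for the ITT-infected population, and the protocol neither assumes nor allows for anything else. The shortfall in the minimum is about 2 to 3 points at a 5% loss, 4.5 points at 10% and just under 10 points at 20%. These loss rates are assumptions, and the shape parameters were inferred from Table 5. Only the linear cell falls below 79% at once. The combined claim of more than 90% fails narrowly at a 10% loss from 74 per arm, but is secure at the planned 98. This is a mismatch between the stated N and the stated population, which should be corrected. It does not show that the design fails its primary objective.

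**What to change.** Define N in Table 5 as ITT-infected subjects. State an assumed exclusion rate, for example from pooled blinded central-confirmation data in this study, noting that hospitalized children may differ from outpatients. Then restate the 79% sentence and the conclusion that Cohort 2 suffices alone: at a 10% loss the minimum would read about 75%. Where the combined figure is quoted, say whether it refers to 74 or 98 per arm before exclusions.

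The cost is a revised table and a few sentences, with a fallback figure a few points less favourable. No added enrollment is needed. If the sponsor preferred to keep 79% as a true minimum, 50 analysed per arm would require randomizing 50/0.95 ≈ 53 per arm at a 5% loss or 50/0.90 ≈ 56 at a 10% loss.
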